Ramucirumab is a fully human IgG1 monoclonal antibody that is a specific and direct inhibitor of VEGFR-2, where it binds to the extracellular VEGF-binding domain with high degree of specificity and affinity, at picomolar dose range. It thus prevents the binding of the VEGF ligand to the VEGF-R2 receptor. In the phase I trial for patients with advanced solid tumors, ($n=37$) ramucirumab demonstrated encouraging early evidence of efficacy at a range of dose levels including the one enrolled patient with biliary cancer who experienced stable disease lasting over 5 months³⁰. Ramucirumab was recently shown to improve survival compared with placebo in advanced gastric cancer, with a median overall survival of 5.2 months in the ramucirumab arm, and 3.8 months in the placebo arm. The main toxicity seen was an increase in hypertension in the ramucirumab group³¹. Additionally, a double-blind, randomized, phase III study of previously treated gastric and gastroesophageal junction cancers included 665 patients randomized to ramucirumab plus paclitaxel versus placebo plus paclitaxel³². In this study, the combination arm showed an improvement in overall survival (9.6 months vs. 7.4 mths, $p=0.017$), providing further rationale for the use of ramucirumab in refractory gastric cancer.

Initial data with ramucirumab in biliary cancer

In the initial 43 patient cohort that was enrolled in this phase II trial, 42 patients with cholangiocarcinoma and gallbladder cancers received treatment. Ramucirumab was well tolerated with 9 grade 3 toxicities including anorexia, dehydration, hypertension, hyponatremia, proteinuria and vomiting. There were no grade 4 toxicities. The median PFS for all patients who received treatment was 2.73 months (95% CI 1.91-8.03 months) and median OS was 6.31 months (95% CI 4.7 months – not reached). The overall response rate was 0% and disease control rate (SD + PR + CR) was 44%. Importantly, 6 patients (13%) were on treatment for > 24 weeks. Of these, 3 were on treatment for at least 44 weeks. In reviewing the genomic data on the 6 patients with prolonged periods of stable disease, we noted that 4 of the 6 harbored mutations in DNA repair pathways (BRCA, FANCA, ARID1A) and 1 patient had an FGFR alteration

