5. PATIENT ELIGIBILITY

Patients will be included in the study based on the following inclusion and exclusion criteria.

INCLUSION CRITERIA

1. Patient must have cholangiocarcinoma, gallbladder cancer or adenocarcinoma on liver biopsy with clinical features consistent with biliary primary/ cholangiocarcinoma.
2. Metastatic or unresectable disease documented on diagnostic imaging studies.
3. Must have received at least one regimen containing gemcitabine chemotherapy.
4. Eastern Cooperative Oncology Group (ECOG) Performance Status of 0 to 1 (Appendix 1).
5. The patient has adequate hepatic function as defined by a total bilirubin ≤ 1.5 mg/dL (25.65 $\mu\text{mol/L}$), and aspartate transaminase (AST) and alanine transaminase (ALT) ≤ 3.0 times the upper limit of normal (ULN; or 5.0 times the ULN in the setting of liver metastases).
6. The patient has adequate hematologic function, as evidenced by an absolute neutrophil count (ANC) $\geq 1000/\mu\text{L}$, hemoglobin ≥ 9 g/dL (5.58 mmol/L), and platelets $\geq 100,000/\mu\text{L}$.

7. The patient does not have:
 - a. Cirrhosis at a level of Child-Pugh B (or worse) or
 - b. Cirrhosis (any degree) and a history of hepatic encephalopathy or clinically meaningful ascites resulting from cirrhosis. Clinically meaningful ascites is defined as ascites from cirrhosis requiring diuretics or paracentesis.
8. The patient has adequate renal function as defined by a serum creatinine ≤ 1.5 times the ULN, or creatinine clearance (measured via 24-hour urine collection) ≥ 40 mL/minute (that is, if serum creatinine is > 1.5 times the ULN, a 24-hour urine collection to calculate creatinine clearance must be performed).
9. The patient's urinary protein is $\leq 1+$ (≤ 30 -100 mg/dl) on dipstick or routine urinalysis (UA; if urine dipstick or routine analysis is $\geq 2+$ (≥ 100 -300 mg/dl), a 24-hour urine collection for protein must demonstrate < 1000 mg of protein in 24 hours to allow participation in this protocol).

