A cycle of therapy may be delayed up to 3 weeks to allow for weather events, patient’s personal emergencies, observation of holidays, or other unforeseen delays that the Investigator deems to be in the best interest of the patient. For any dose interruptions, re-initiation of therapy may be delayed for a maximum of 30 days to allow recovery from any toxicity. In exceptional cases where subjects are responding, re-initiation of therapy after missing > 30 consecutive days of treatment may be done on a case-by-case basis after confirmation with the Primary Investigator.

Toxicity will be graded according to the NCI CTCAE, Version 4.0 (which is available at: http://ctep.info.nih.gov/protocolDevelopment/electronic_applications/ctc.htm). For any event which is apparent at baseline, the dose modification will apply according to the corresponding shift in toxicity grade if the investigator feels this is appropriate, (e.g. if a patient has grade 1 asthenia at baseline which increases to grade 2 during treatment, this will be considered as a shift of 1 grade and treated as a grade 1 toxicity for dose modification purposes).

Dose modifications of ramucirumab will be done based on the specific toxicity. Once a dose of

any study drug has been reduced, it should not be increased at a later time. Reasons for dose modifications or delays, the supportive measures taken, and the outcome will be documented in progress notes. Growth factors may be used to treat hematologic toxicity and will not constitute a dose reduction. A maximum of a 3-week treatment delay is permitted to allow recovery of toxicities.

Table 3: Dose Levels

Dose Level	Ramucirumab (mg/kg)
0 – baseline	8
-1	6
-2	5

Hematologic Toxicity

Though myelosuppression is expected to be rare, in the event dose modifications are required at the beginning of a cycle due to hematologic toxicities, dose of ramucirumab may be adjusted as detailed below.

Table 4: Dose Modifications for Day 1 of Each Cycle (Hematologic Toxicity)

ANC		Platelets	Timing
≥ 1,500 cells/mm ³	AND	≥ 75,000/uL	Treat on time
< 1,500 cells/mm ³	OR	< 75,000/uL	Delay by 1 week intervals until recovery

Special Instructions Regarding Treatment of Chemotherapy-related Toxicity

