Dose modification or delay may occur in the setting of lower Grade toxicity if the treating physician believes that it is in the interest of a subject’s safety. Alopecia and nausea and/or vomiting that can be controlled by antiemetics do not require dose modification or interruption. No dose reduction or interruption will be required for anemia as it can be satisfactorily managed by transfusions. Dose reductions for non-hematologic toxicity should be as below.

Table 5: Dose Modifications for Ramucirumab on Day 1 of Each Cycle (Non-Hematologic Toxicity)*

Toxicity/Dose Held	Ramucirumab dose this cycle
Grade 0-2 toxicity	Same as Day 1 previous cycle
Grade 3 toxicity	Decrease ramucirumab to next lower dose level
Grade 4 toxicity	Off protocol treatment
Dose held in 2 previous consecutive cycles	Decrease ramucirumab to next lower dose level and continue throughout the rest of treatment

* Drug-specific toxicities are explained in greater detail below with appropriate modifications

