8. CRITERIA FOR REMOVAL FROM THE STUDY

Subjects who meet the following criteria should be discontinued from study treatment:

- Disease progression
- Intercurrent illness that prevents further administration of treatment
- Unacceptable adverse event(s) as determined by the treating physician
- Patient decides to withdraw from the study
- General or specific changes in the patient's condition render the patient unacceptable for further treatment in the judgment of the investigator.

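### The optional baseline-shift rule in section 6 has no Grade 4 exception, so a Grade 4 event already present at baseline can bypass Table 5's off-treatment row

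*Combined protocol and SAP*

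**What the plan says.** Under Dose Modifications and Toxicity Management, section 6 introduces the shift rule with "For any event which is apparent at baseline" and continues that "the dose modification will apply according to the corresponding shift in toxicity grade if the investigator feels this is appropriate". The only example is asthenia rising from Grade 1 to Grade 2: "this will be considered as a shift of 1 grade and treated as a grade 1 toxicity for dose modification purposes".

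Table 5, the dose-modification table for non-hematologic toxicity, keeps the dose the same for Grades 0 to 2, lowers it by one level for Grade 3, and for Grade 4 gives "Off protocol treatment". Its footnote adds: "Drug-specific toxicities are explained in greater detail below with appropriate modifications". Those details are in sections 6.2 to 6.7, which set discontinuation criteria for infusion reactions, hypertension, thrombotic events, bleeding, proteinuria and gastrointestinal perforation.

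Section 8 lists the general reasons for stopping treatment. The one closest to this point is "Unacceptable adverse event(s) as determined by the treating physician".

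**The concern.** Two rules in the same section conflict. Table 5 states the Grade 4 stop without qualification. The shift rule replaces the grade reached with the change in grade, sets no ceiling, and does not say which rule prevails when the grade reached would require a stop. The example is low grade and does not settle the matter.

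What is at stake is patient safety. A permitted reading allows further ramucirumab, at a reduced or even unchanged dose, after a Grade 4 non-hematologic event. Whether the patient stops would then depend on the investigator's choice, in a row of Table 5 that offers no choice.

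The gap mainly concerns toxicities without a section of their own. Raised transaminases are one example. Inclusion criterion 5 in section 5 admits AST and ALT up to 3.0 times the upper limit of normal, "or 5.0 times the ULN in the setting of liver metastases", so an elevation can be present at baseline, and sections 6.2 to 6.7 contain no hepatic rule.

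Two neighbouring features are not defects: the milder handling of Grade 3 events under the shift rule, and the use of actual grades for toxicity monitoring in section 10.4.

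**Working it through.** The plan gives no figure to reproduce here, so the check applies one rule to the other.

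**Inputs**
- Shift rule and its example: section 6.
- Actions by grade: Table 5.
- Dose levels of 8, 6 and 5 mg/kg: Table 3.
- Initial cohort of 43 enrolled and 42 treated, with the statement "There were no grade 4 toxicities": section 2, initial data with ramucirumab in biliary cancer.
- Expansion of 10 patients: inclusion criterion 15. Maximum of 60 patients: section 10.1.

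**Step 1: the formula.** Handled grade = on-study grade − baseline grade. The protocol's own example fits: 2 − 1 = 1, handled as Grade 1.

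**Step 2: a first Grade 4 non-hematologic event at 8 mg/kg.**

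| Baseline grade | Shift | Table 5 row entered | Next dose | Next dose by actual grade |
|---|---|---|---|---|
| 1 | 4 − 1 = 3 | Grade 3 | 6 mg/kg (6/8 = 75%) | none, off treatment |
| 2 | 4 − 2 = 2 | Grade 0–2 | 8 mg/kg (100%) | none, off treatment |
| 3 | 4 − 3 = 1 | Grade 0–2 | 8 mg/kg (100%) | none, off treatment |

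For any baseline grade of 1 or more, the shift is at most 4 − 1 = 3. The Grade 4 row therefore cannot be reached whenever the investigator uses the shift for an event present at baseline.

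**Step 3: does the shift rule extend to stopping?** The Grade 4 stop is a row of Table 5, whose title is about dose modifications, and the shift rule governs the grade used for that purpose. Nothing in the text takes the Grade 4 row out of its scope.

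**Step 4: how many patients could be affected.** With 0 Grade 4 toxicities in 42 patients, the one-sided 95% upper limit is 1 − 0.05^(1/42) = 0.0688, or 6.9%.
- Ten-patient expansion: 10 × 0.0688 = 0.69 expected patients at that limit.
- If every place between the 43 already enrolled and the maximum of 60 were filled: 17 × 0.0688 = 1.2.

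Both are ceilings for any Grade 4 toxicity. The patients of concern are a subset: the same event must have been present at baseline, and the investigator must have chosen the shift.

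**The case against.** The strongest case on the other side is that this is a deliberate, discretionary rule with several safeguards around it.

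- **It is optional and coherent.** The dosing scheme addresses drug-related toxicity, so discounting the part of an event that predates the drug makes sense. This stands as a defence of the shift rule in general. It does not explain why the discretion should extend to the one grade at which Table 5 stops treatment.
- **Other text allows caution.** Section 6 calls for management by standard medical practice. The text above Table 5 lets the physician reduce or delay at lower grades for safety. Section 8 also covers intercurrent illness and deterioration in the patient's condition. A low handled grade therefore never obliges anyone to continue at the same dose. This makes harm unlikely, since an investigator would have to choose the shift and then decline every other option. But these provisions rest largely on judgment, and none restores an automatic Grade 4 stop.
- **The toxicities of main concern have their own stopping criteria.** This largely stands. Sections 6.2 to 6.7 are better read as prevailing over the shift rule, because section 6 ties dose changes to the specific toxicity and the Table 5 footnote points to those sections. The text does not say so outright.
- **The transaminase example is incomplete.** The documents give entry limits as multiples of the upper limit of normal but no CTCAE cut-offs, so the baseline grade that those limits represent cannot be shown from them. The example shows only that an elevation may be present at entry with no drug-specific rule to govern it.
- **The 6.9% limit does not measure the gap itself.** Correct. It bounds all Grade 4 toxicity, and section 2 does not say whether its count is all-cause or treatment-related. It serves only as a ceiling.

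**Conclusion.** The concern holds as a minor patient-safety point. Whenever the shift rule is used for an event with a baseline grade of 1 or more, Table 5's Grade 4 stop is bypassed: the next dose is 75% of the starting dose for baseline Grade 1 and 100% for baseline Grade 2 or 3, where the actual grade would mean no further dose.

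This rests on a literal reading of the shift rule, on a first Grade 4 event at the 8 mg/kg level, and on a toxicity outside sections 6.2 to 6.7. The expected number of affected patients is very small, below 0.69 in the ten-patient expansion even at the upper confidence limit, if the initial cohort's experience carries over to those patients.

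Sample size and operating characteristics are unaffected. Section 10.4 states no shift adjustment, so a qualifying Grade 4 event in the first 28 days still counts there. That rule stops enrollment, however, and does not take the individual patient off the drug.

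**What to change.** Add one sentence after the shift rule in section 6:

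*The baseline-shift rule does not apply to any event that reaches Grade 4, or to any event for which sections 6.2–6.7 require discontinuation; in these cases the actual CTCAE grade, or the criterion stated in that section, governs.*

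Leave the shift rule unchanged for Grade 1 to 3 events handled under Table 5.

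The cost is one sentence at the next amendment, with no extra patients, visits or procedures. The downside is a small loss of discretion, for example over an asymptomatic Grade 4 laboratory value in a patient whose baseline was already raised. Table 5 on its own terms already requires a stop in that case.

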6.1 G-CSF Administration

The exact dosage amount and schedule for G-CSF support will be left to the treating physician’s discretion. A recommended approach would be to administer G-CSF 5

mcg/kg/day (rounded to the nearest vial size per investigator's standard of care) 24 hours after chemotherapy until recovery to the predetermined neutrophil count.

6.2 Infusion-related reactions

Infusion reactions are defined according to the NCI-CTCAE Version 4.02 definition of infusion-related reactions, (General disorders and administration site conditions, p. 23). Symptoms occurring during or following infusion of investigational therapy may also be defined according to adverse event categories such as allergic reaction, anaphylaxis, or cytokine release syndrome (Immune system disorders, p. 26). In the setting of symptoms occurring during or following infusion of investigational therapy, the adverse event term "Infusion-related Reaction" and any additional terms (including those not listed here) that best describe the event should be used. Those described above should be graded as follows:

Table 6: NCI-CTCAE v 4.02 Infusion-related Reactions

Adverse Event	Grade 1	Grade 2	Grade 3	Grade 4	Grade 5
Infusion-related reaction	Mild transient reaction; infusion interruption not indicated; intervention not indicated	Therapy or infusion interruption indicated but responds promptly to symptomatic treatment (eg, antihistamines, NSAIDS, narcotics, I.V. fluids); prophylactic medications indicated for ≤ 24 hrs	Prolonged (eg, not rapidly responsive to symptomatic medication and/or brief interruption of infusion); recurrence of symptoms following initial improvement; hospitalization indicated for clinical sequelae	Life-threatening consequences; urgent intervention indicated	Death
Definition: A disorder characterized by an adverse reaction to the infusion of pharmacological or biological substances.					
Allergic reaction	Transient flushing or rash, drug fever <38 degrees C (<100.4 degrees F); intervention not indicated	Intervention or infusion interruption indicated; responds promptly to symptomatic treatment (eg, antihistamines, NSAIDS, narcotics); prophylactic medications indicated for ≤ 24 hrs	Prolonged (eg, not rapidly responsive to symptomatic medication and/or brief interruption of infusion); recurrence of symptoms following initial improvement; hospitalization indicated for clinical sequelae (eg, renal impairment, pulmonary infiltrates)	Life-threatening consequences; urgent intervention indicated	Death
Definition: A disorder characterized by an adverse local or general response from exposure to an allergen.					
Anaphylaxis	-	-	Symptomatic bronchospasm, with or without urticaria; parenteral intervention indicated; allergy-related edema/angioedema; hypotension	Life-threatening consequences; urgent intervention indicated	Death
Definition: A disorder characterized by an acute inflammatory reaction resulting from the release of histamine and histamine-like substances from mast cells, causing a hypersensitivity immune response. Clinically, it presents with breathing difficulty, dizziness, hypotension, cyanosis, and loss of consciousness and may lead to death.					
Cytokine release syndrome	Mild reaction; infusion interruption not indicated; intervention not indicated	Therapy or infusion interruption indicated but responds promptly to symptomatic treatment (eg, antihistamines, NSAIDS, narcotics, I.V. fluids); prophylactic medications indicated for ≤ 24 hrs	Prolonged (eg, not rapidly responsive to symptomatic medication and/or brief interruption of infusion); recurrence of symptoms following initial improvement; hospitalization indicated for clinical sequelae (eg, renal impairment, pulmonary infiltrates)	Life-threatening consequences; pressor or ventilator support indicated	Death
Definition: A disorder characterized by nausea, headache, tachycardia, hypotension, rash, and shortness of breath; it is caused by the release of cytokines from the cell.					

If a patient experiences a Grade 1 or 2 infusion reaction, the infusion rate should be decreased for the duration of the infusion and all subsequent infusions, as directed in the protocol. In addition, patients with Grade 1 and 2 infusion reactions should be treated according to standard medical practices. After a Grade 1 or 2 infusion reaction, patients should be premedicated with antihistamines, steroids, acetaminophen, etc, as appropriate for subsequent infusions.

A Grade 3 or 4 infusion reaction will require immediate treatment, including the use of epinephrine, bronchodilators, and/or glucocorticoids for symptomatic bronchospasm, I.V. fluids and/or pressors for hypotension, and immediate and permanent discontinuation of ramucirumab with appropriate supportive care.

Consistent with usual medical practice, selected parenteral medications may be utilized for Grade 2 infusion-related reactions as detailed below.

The following are general treatment guidelines for ramucirumab infusion-related reactions:

Grade1

- Slow the infusion rate by 50%
- Monitor the patient for worsening of condition
- For subsequent infusions, continue to premedicate with diphenhydramine hydrochloride 50 mg I.V. (or equivalent); additional premedication may be administered at the investigator's discretion

Grade2

- Stop the infusion
- Administer diphenhydramine hydrochloride 50 mg I.V. (or equivalent), acetaminophen 650 mg orally for fever, and oxygen
- Resume the infusion at 50% of the prior rate once the infusion reaction has resolved or decreased to Grade 1; the infusion duration should not exceed 2 hours
- Monitor for worsening of condition
- For subsequent infusions, continue to premedicate with diphenhydramine hydrochloride 50 mg I.V. (or equivalent); additional premedication may be administered at the investigator's discretion

For a second Grade 1 or 2 infusion reaction, administer dexamethasone 8-10 mg I.V. (or equivalent); then, for subsequent infusions, premedicate with diphenhydramine hydrochloride 50 mg I.V. (or equivalent), acetaminophen 650 mg orally, and dexamethasone 8-10 mg I.V. (or equivalent).

Grade 3

- Stop the infusion and disconnect the infusion tubing from the patient
- Administer diphenhydramine hydrochloride 50 mg I.V. (or equivalent), dexamethasone 10 mg I.V. (or equivalent), bronchodilators for bronchospasm, and other medications/treatment as medically indicated
- Patients who have a Grade 3 infusion reaction will not receive further ramucirumab treatment, but will continue to be followed on the protocol

Grade 4

- Stop the infusion and disconnect the infusion tubing from the patient
- Administer diphenhydramine hydrochloride 50 mg I.V. (or equivalent), dexamethasone 10 mg I.V. (or equivalent), and other medications/treatment as medically indicated
- Give epinephrine or bronchodilators as indicated
- Hospital admission for observation may be indicated
- Patients who have a Grade 4 infusion reaction will not receive further ramucirumab treatment, but will continue to be followed on the protocol

6.3 Hypertension

If a patient develops hypertension during the study, he/she should be treated with antihypertensive medications according to standard medical practice.

Grade<3

- If the hypertension is not associated with symptoms, continue ramucirumab and initiate anti-hypertensive therapy.

- If the hypertension is associated with symptoms, hold ramucirumab until symptoms resolve and initiate anti-hypertensive therapy.
- If ramucirumab therapy is held more than once for hypertension (ie, symptomatic hypertension, markedly elevated blood pressure unresponsive to anti-hypertensive therapy), the dose of ramucirumab should be reduced upon re-treatment (refer to protocol for dose and frequency). A second dose-reduction (refer to protocol for dose and frequency) should be undertaken if an additional postponement of therapy is required.

Grade 3 (systolic BP \geq 160 mmHg or diastolic BP \geq 100 mmHg; medical intervention indicated; more than one drug or more intensive therapy than previously used indicated)

- For Grade 3 hypertension not associated with symptoms, continue ramucirumab with more intensive anti-hypertensive therapy. If systolic BP remains \geq 160 or diastolic BP \geq 100 mmHg $>$ 2 weeks after initiation of additional anti-hypertensive therapy, hold ramucirumab while continuing appropriate anti-hypertensive therapy.
- If the hypertension is associated with symptoms, hold ramucirumab until symptoms resolve and initiate anti-hypertensive therapy.
- If ramucirumab therapy is held more than once for hypertension (ie, symptomatic hypertension, markedly elevated blood pressure unresponsive to anti-hypertensive therapy), the dose of ramucirumab should be reduced upon re-treatment. A second dose-reduction should be undertaken if an additional postponement of therapy is required.

Grade 4 or refractory

Patients with Grade 4 hypertension (life-threatening consequences, eg, malignant hypertension, transient or permanent neurologic deficit, hypertensive crisis; or urgent intervention indicated) or patients whose hypertension is poorly controlled ($>$ 160 mmHg systolic or $>$ 100 mmHg diastolic for $>$ 4 weeks) despite appropriate oral medication ($>$ 2 oral agents at maximum tolerated dose) will be discontinued from study therapy.

